Aim 1: Intervention development and refinement (ORBIT Phase 1): The first aim of the project is to translate positive psychology theory and research into a 6-week, group-based positive psychology for PA promotion (PPPA) intervention for low-active overweight or obese adults, delivered at local YMCAs, and supplemented with text messaging. The in-person session and text-messaging protocol will be based on the team's previous and ongoing work developing and implementing positive psychology and smoking cessation interventions ([name], [name]), as well as our expertise in exercise promotion interventions ([name]; [name]). We will deliver the intervention prototype among a cohort of 10 low-active (< 60 min/week of structured PA) overweight or obese adults (≥ 18 years; BMI 25-40). Participants and clinician-investigators will provide ongoing feedback regarding their experiences with application of the intervention in an iterative development process to refine the protocol, improve the utility of the intervention and modify intervention materials. The milestone for Phase 1 is a finalized PPPA intervention protocol by month 6 of year 1.

Aim 2: Preliminary testing (ORBIT Phase 2): The second aim of the project is to test proof-of-concept and feasibility of PPPA. This will be accomplished in the context of a randomized pilot study among 60 low-active overweight or obese adults at local YMCAs. In an additive design, participants will be randomized in a 2:1 ratio to PPPA versus a control intervention including only the standard PA promotion components of the PPPA intervention (i.e., PA education, self-monitoring, and goal-setting), with equal frequency of staff contact and text message delivery. All participants will be followed for 6 months, including the 6-week treatment period, and will receive a 6-month YMCA membership to equate access to PA facilities. We hypothesize that participants in PPPA, relative to the standard PA intervention will: demonstrate equal or greater session treatment retention and satisfaction (H1); and more min per week of PA as measured by accelerometry at immediate post-treatment (week 7) and weeks 13 and week 26 (H2).

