PPPA model of PA promotion. In the PPPA model, success in maintaining regular PA is influenced by perceived physical and mental health benefits of PA, overcoming negative associations with PA, social and environmental factors, and personal factors such as commitment to PA, optimism, satisfaction with the past, and positive emotions. Examples of how PPPA will address each of these areas will be provided. Participants will be told that the combination of positive psychology strategies and regular PA can help develop and enhance pleasure, happiness, and meaning in life. **Positive introductions.** PPPA will begin by introducing the concept of signature strengths and how those can be important in adhering to a program of regular PA.

Participants are provided feedback about their 5 signature strengths based on the Values in Actions Survey⁹⁷ and asked to share (via texting) how they demonstrated one of their strengths. **Using signature strengths.**

Treatment providers highlight the role that signature strengths play in leading an engaged life and assign participants to find new ways to employ their signature strengths in their daily life. This treatment element has been empirically demonstrated to decrease negative affect and increase happiness.⁸² In PPPA, participants are also asked to consider how they can employ their signature character strengths to help them manage barriers to regular PA. **Three good things.** Participants are instructed to text about three good things that happened each day and their causes. This exercise has been shown to have rapid and lasting effects on reducing negative affect and increasing happiness⁸² and has been employed successfully via text messaging.⁹⁸ **Savoring.** Treatment providers introduce the concept of savoring positive experiences.

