Intervention feasibility and acceptability: We will record PPPA session attendance and responses to the evening text-messages as objective indices of feasibility and acceptability. Retention will be coded as a dichotomous variable with participants who complete the sixth and final treatment session characterized as treatment "completers" and those not attending the final session as "non-completers." Participants will complete a Treatment Strategies Questionnaire at sessions 2-6, which will assess frequency of use of specific PPPA strategies in the past week such as planning opportunities for PA and completing the 3 Good Things exercise.¹⁰⁸ Responses to the questions will be used to inform the treatment feedback process. Satisfaction will also be assessed with the Client Satisfaction Questionnaire, an 8-item questionnaire that will be administered at the 7-week follow-up to assess participant satisfaction with provided services (CSQ-8).¹⁰⁹ **Positive psychology measures and putative mediators:** The Values in Action Survey⁹⁷ will be administered to all participants at baseline, and participants will receive feedback on their 5 "Signature Strengths" derived from this measure.^{81,82} The following putative mediators will be assessed at mid-treatment (session 3), post-treatment (week 7), and 13-week follow-ups. Short-term changes in positive and negative affect will be assessed with the Positive and Negative Affect Scale.¹¹⁰ Trait optimism will be assessed with the well-validated revised Life Orientation Scale.¹¹¹ Subjective happiness and subjective well-being will be assessed with the 4-item Subjective Happiness Scale¹¹² and the 5-item Satisfaction with Life Scale.¹¹³ Social support will be assessed at baseline and follow-ups using the 13-item Social Support for Exercise Scale.¹¹⁴ Finally, PA enjoyment will be assessed with the 18-item Physical Activity Enjoyment Scale.¹¹⁵

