C.2.i. Intervention refinement. During the initial PPPA intervention group, the intervention manual and materials will be refined based on an iterative treatment development process. After each of the sessions is completed, participants will complete brief questionnaires on perceived session utility and their use of PPPA strategies in the past week. Open-ended questions will also assess the utility and acceptability of the treatment sessions and exercises. Intervention refinement will also be based on investigators' weekly reviews and discussion of the audio-recorded sessions. This will lead to a revised PPPA manual going into Phase 2.

C.3. Additional procedures for Aim 2: Preliminary testing (ORBIT phase 2).

Procedures for Aim 2 will be the same as Aim 1, with the following exceptions:

C.3.a. Recruitment, enrollment, and randomization. We will recruit 60 participants who will be randomized at a 2:1 ratio to PPPA treatment versus **standard PA promotion (SPA)** in order to focus resources on the PPPA program while still including a comparison for preliminary testing. We will run 4 groups of PPPA and 2 groups of SPA, with 10 participants per group. Urn randomization will be used to balance on sex and BMI.

C.3.b. PPPA condition. The PPPA condition will follow the revised treatment manual and text messaging program, based on feedback from Aim 1, but will follow the basic themes and procedures noted above.

C.3.c. SPA condition. The SPA condition will consist of the **core PA promotion content** (see above). To equate for session duration, additional information on health and wellness will be delivered by the staff, including topics such as skin care, alcohol use, and heart health. **Text messages** for the SPA condition will consist of reminders to engage in PA and other general motivational messages, thus controlling for total number of text messages. Because all of the PA-related content in the SPA condition will also be provided in the PPPA condition, this is essentially *an additive design, with an equal contact control*.

C.3.d. Additional 6-month follow-up and 6-month YMCA membership. For both conditions, YMCA memberships will be extended for 6 months, and an additional assessment will take place at month 6 (wk 26).

C.4. Participant retention, compliance, and incentives

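### The plan contradicts itself on whether SPA controls receive the signature-strengths feedback that it lists as PPPA content

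*Combined protocol and SAP*

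**What the plan says.** **Measures.** C.2.h states that the Values in Action Survey "will be administered to all participants at baseline, and participants will receive feedback on their 5" signature strengths. The Measures text under Protection of Human Subjects, section 1.a, repeats this. Neither place mentions study arm.

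**Intervention content.** C.2.d places the same feedback under positive psychology content, in the opening exercise (Positive introductions): "Participants are provided feedback about their 5 signature strengths based on the Values in Actions Survey". The next exercise, Using signature strengths, builds on it by asking participants to find new ways to apply those strengths.

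**Carry-over to Aim 2.** C.3 opens with "Procedures for Aim 2 will be the same as Aim 1, with the following exceptions". The exceptions cover recruitment and randomisation (C.3.a), the revised PPPA manual and texts (C.3.b), SPA session content and texts (C.3.c), and the 26-week visit with the longer membership (C.3.d).

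**Control definition.** The Aim 2 statement, like the opening summary, describes a "control intervention including only the standard PA promotion components of the PPPA intervention", namely education, self-monitoring and goal-setting. C.3.c gives SPA the core activity content and adds filler: "To equate for session duration, additional information on health and wellness will be delivered by the staff". It lists no positive psychology content.

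**The concern.** Aim 1 has one arm, so giving the survey and feedback to everyone there does no harm. The difficulty arises when that text is inherited by a two-arm trial. The comparison is additive: positive psychology content is meant to be the only difference between arms. A baseline procedure that hands part of that content to the controls blurs the contrast.

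C.5 says Aim 2 will concentrate on effect sizes, and the Secondary Aim says the work sets the stage for a later trial powered on main effects and mediation. Affect, happiness and life satisfaction are the outcomes closest to the feedback; minutes of activity are further along the causal path. Feedback cannot be withdrawn once given. If every control receives it, no analysis can recover the intended contrast. If staff resolve the conflict differently from group to group, exposure varies, and nothing in the plan records it.

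**Working it through.** **1. Numbers exposed under the literal reading.** From C.3.a: 4 PPPA groups × 10 = 40, 2 SPA groups × 10 = 20, total 60, ratio 2:1. This reproduces the split in C.5. All 20 controls would be affected.

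**2. The passages side by side.**

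| Question | Points to SPA receiving feedback | Points to SPA not receiving it |
|---|---|---|
| Who is covered? | C.2.h and section 1.a: all participants, no arm limit | C.2.h is written for single-arm Aim 1 |
| What carries into Aim 2? | C.3: everything not listed as an exception; the survey is not listed | C.3.c is an exception and redefines what SPA consists of |
| What kind of item is it? | C.2.h places it among the measures | C.2.d places it in PPPA content |
| What is the control? | – | Summary, Aim 2 statement: standard components only |

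**3. Does the Measures section apply to SPA at all?** It must. C.5 compares attendance, satisfaction, retention, MVPA and the mediators between arms, and C.2.h is where these are defined. The survey sentence sits among them with nothing to set it apart. C.2.e, also in the Aim 1 text, already refers to manuals for both PPPA and SPA.

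**4. What exactly would be shared?** The survey and the feedback on five strengths. The task of texting about a strength belongs to the PPPA texts, which C.3.c replaces for SPA. No passage assigns SPA the Using signature strengths exercise or any later exercise. Completing the survey as a measure in both arms contradicts nothing; the conflict concerns the feedback.

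**5. Size.** If feedback in SPA removed a fraction f of a true standardised difference d, the observed difference would be (1 − f) × d. The documents give no value for f, including whether it exceeds zero. Purely to show scale, take d = .20 and .34 (the two well-being figures from the meta-analysis of randomised trials in A.4) and assume f = 10% to 30%:

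- d = .34: .34 × .90 = .31, down to .34 × .70 = .24; a shift of .03 to .10.
- d = .20: .20 × .90 = .18, down to .20 × .70 = .14; a shift of .02 to .06.

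For comparison, at 40 versus 20, with no dropout and no group clustering, SE(d) ≈ √(1/20 + 1/40) = .274. The shifts are about .02/.274 = 0.07 to .10/.274 = 0.37 of one standard error. These figures rest wholly on the assumed f, and on A.4 effects that were not estimated for PPPA.

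**The case against.** The strongest reply is that a sensible reader would not give SPA the feedback. C.2.h describes a single-arm phase, so its participants are PPPA participants. C.3.c is a specific exception that removes positive psychology content as a group, and a specific rule normally overrides a general carry-over clause. Literal carry-over also fails elsewhere: C.2.h speaks of PPPA session attendance, which cannot apply to SPA as worded. This has real weight. It rules out saying that the controls do receive the feedback, but it does not remove the conflict. C.3.c addresses sessions and texts, whereas the feedback sentence stands among baseline measures that otherwise have to carry over.

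A reader might also infer that controls would receive a component of proven effect, because C.2.d says: "This treatment element has been empirically demonstrated to decrease negative affect and increase happiness". The text does not support that. The statement is attached to the Using signature strengths exercise, and no effect is claimed for feedback alone.

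A further inference might be that the Treatment Strategies Questionnaire, given at sessions 2 to 6, contaminates SPA because it covers "specific PPPA strategies in the past week such as planning opportunities for PA and completing the 3 Good Things exercise". It is true that neither C.2.h nor section 1.b (Sources of Materials) limits these items by arm. But asking how often an exercise was used does not deliver it, planning for activity is core content, and the item wording is not given. Asking both arms can serve as a check for contamination.

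Finally, C.5 already acknowledges large standard errors at this sample size, and any plausible dilution may be small beside them. That is fair as to size. A systematic shift caused by a drafting conflict is still avoidable, whereas sampling error is not.

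**Conclusion.** The concern holds as a contradiction about what the control arm receives. C.2.h and section 1.a, joined to the carry-over clause in C.3, give SPA the feedback on a literal reading; the opening summary, the Aim 2 statement and C.3.c imply that it does not. The conclusion rests on the wording alone and needs no numerical assumption.

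If the literal text is followed, all 20 controls receive part of the tested content. Provided the feedback has some benefit, the bias would probably be toward no difference on affect and happiness, with any effect on MVPA less direct. The documents do not allow its size to be derived, and the fractions shown above are not estimates. The questionnaire point is secondary and does not require correction.

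**What to change.** Reconcile the passages before Aim 2 enrolment:

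- In C.2.h and in the matching Measures text of section 1.a, limit the feedback sentence to PPPA participants.
- In C.3.c, and its counterpart in section 1.a, add that SPA participants complete the Values in Action Survey at baseline, so that assessment is the same in both arms, but receive no signature-strengths feedback until after the week 26 assessment.

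The cost is a change of wording in a few places and a delay in feedback to 20 people.

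Optional: state whether SPA answers the PPPA-strategy items of the Treatment Strategies Questionnaire. Keeping them provides contemporaneous information on contamination. Restricting SPA to core activity items avoids naming PPPA exercises to controls but loses that information, and asking once after week 26 would come about 26 − 6 = 20 weeks after the last session. Either choice is defensible if stated.

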Participants are asked to savor at least two experiences each day for one week and text back their response to evening text prompts regarding homework completion. **Active/constructive responding.** Participants are instructed to listen carefully when people they care about report good events. They are instructed to stop and go out of their way to respond actively and constructively to these events and to keep a record of these experiences via nightly texting. **Commitment and gratitude discussion.** This exercise involves selecting an important support for PA, discussing with that person the reason one is grateful to them and the reasons they appreciate them, and asking for specific support for increasing and maintaining regular PA.^{81,82} **Maintenance of happiness.** In the final session, participants discuss their experiences with PPPA and generate ways that they can modify these experiences in order to keep using them in their lives. They then choose one or two exercises to continue over the following months after treatment.

Text messaging: Participants in PPPA will receive daily texts. Morning texts provide static messages relevant to a given PPPA exercise, while evening texts are interactive and ask for open-ended descriptions of what participants did to complete that day's PPPA exercise, with a reminder sent after 1 hour if no response is received. These responses are tabulated for the counselor. Text messages specific to a PPPA exercise are initiated at the respective counseling session at which that PPPA exercise is introduced by texting a key word, e.g., 'Savor' to initiate the savoring texts. The PPPA exercise continues each day following the session until that exercise is replaced by a new exercise. At session 6, participants choose which PPPA exercises they want to continue and receive texts based on their choice for an additional 2 weeks. Participants are also given forms for completing exercises on paper if they prefer to write longer responses or won't have cell phone access. **Text messaging platform.** We will build on the text-messaging platform developed by Co-I [name] and currently being used by [name] and [name].⁹⁹ This

program enables users to request additional support messages and uses two-way texting. This beta version has been successfully piloted, allowing us a quick time to start-up.

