C.2.e. Interventionist characteristics and training. The characteristics of the interventionist have implications for ultimate dissemination of the Positive Psychology for PA (PPPA) program should it show initial efficacy. A bachelor's-level RI will conduct the treatment, with oversight from the investigative team. The RI will be similar in training and experience to the community-level staff that we expect would ultimately deliver the treatment in a future effectiveness trial and upon dissemination of the program. Treatment manuals will be developed to ensure consistent delivery of the PPPA and Standard PA promotion (SPA) interventions. The RI will practice the treatment protocol with other staff and students until it is delivered consistently.

C.2.f. Treatment fidelity. A treatment fidelity checklist will be created for each session and completed at the end of each session by the RI. Additionally, all treatment sessions will be audio-recorded. Review of recordings along with a second completion of the checklist will be split among [name], [name], and [name], who will meet weekly with the RI to discuss any deviations from the treatment protocol. Although we do not expect deviations from the protocol, any such deviations will be addressed by the PI, with the RI retrained as needed. Weekly meetings will also be used to assess strengths and weaknesses of treatment components and suggest revisions to the protocol that will be implemented in the next phase of research (see below).

C.2.g. Assessment timeline. Assessments will be conducted at baseline, ongoing during the 6-week PPPA program, at week 7 (one week after the final PPPA intervention session) and at week 13 (3-month follow-up).

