Aim 2. We will focus on determining **effect sizes** for PPPA rather than strict statistical significance testing. At the same time, we are well aware of the dangers of relying exclusively on small-scale pilots to determine the promise of novel treatment approaches,¹¹⁹ as estimates from small samples tend to have large standard errors. Thus our hope is that we find a pattern of results that is supportive of the experimental treatment. Similar PPIs have shown medium to large effect sizes on depressive symptoms, positive affect, and happiness. Effect size estimates will include Cohen's *d* (for unadjusted between-group comparisons) and f^2 (for longitudinal multivariate models of treatment effect). For the purpose of estimating the effects of treatment on both MVPA and the putative mediators, we will fit a series of mixed effects regression models in which, for example, min/week of objectively measured MVPA at post treatment, and at 13 and 26 weeks will be simultaneously regressed on treatment group, baseline MVPA and variables not balanced by randomization. Models will allow for estimating both effects of treatment on MVPA post treatment, as well as maintenance of MVPA from 7 weeks through 6m. A similar strategy will be used to estimate effect sizes with respect to treatment effects on the putative mediators. We believe a sample size of 60 (40 intervention versus 20 control) should allow adequate examination of PPPA intervention effect sizes while staying within the scope of a developmental project. We recognize that only medium to large effect sizes will be likely to attain statistical significance with an unbalanced sample of this size. **Feasibility and acceptability:** Between-group differences for continuous measures (number of sessions attended and client satisfaction scores at post-treatment) will be conducted using analysis of variance and chi-squared analyses for dichotomous variables (treatment retention). We anticipate that treatment attendance and completion will either be equal or will be higher in the PPPA condition.

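### The Aim 2 tests of H1 treat participants as independent although treatment is given in six groups nested within arm; their standard errors are too small if outcomes correlate within a delivery group

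*Combined protocol and SAP*

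**What the plan says.** Section C.3.a randomizes individuals 2:1, with urn randomization balancing sex and BMI, and then sets the delivery format: "We will run 4 groups of PPPA and 2 groups of SPA, with 10 participants per group". The Protection of Human Subjects section repeats this. Both arms meet weekly for six weeks.

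The Aim 2 analysis is in C.5:

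- **H1 (feasibility and acceptability).** The hypothesis is that PPPA participants will "demonstrate equal or greater session treatment retention and satisfaction (H1"). Comparisons of sessions attended, CSQ-8 satisfaction and retention are to be "conducted using analysis of variance and chi-squared analyses for dichotomous variables (treatment retention").
- **Effect sizes.** Cohen's d is planned "for unadjusted between-group comparisons". No standard error or interval is specified for it.
- **MVPA and putative mediators.** In the mixed effects models the outcomes "will be simultaneously regressed on treatment group, baseline MVPA and variables not balanced by randomization". The random effects are not described.
- **Sample size.** The plan comments: "We recognize that only medium to large effect sizes will be likely to attain statistical significance with an unbalanced sample of this size".

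Neither the analysis text nor the missing-data text after it mentions delivery group, cohort or branch, an ICC or a design effect. In C.5, between-group and treatment group refer to study arm.

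**The concern.** Randomizing individuals does not make their outcomes independent once they are treated together. Members of a delivery group share sessions, peers and timing, and the H1 outcomes (attendance, completing the sixth session, satisfaction with the service) arise in those sessions. Because each group belongs to one arm, variation between delivery groups passes into the arm difference. With four groups against two it averages out only partly. An analysis of 60 independent people leaves that variation out of the standard error.

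H1 is a claim of equal or greater retention and satisfaction. What is at stake is therefore mainly overstated precision: the data could appear to exclude worse PPPA retention more firmly than they do. A later trial planned from these results could inherit the same overconfidence.

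**Working it through.** **Inputs from the documents.** Six groups of m = 10; 4 × 10 = 40 PPPA and 2 × 10 = 20 SPA; total 60, ratio 2:1. This agrees with the sample size in C.5. Expected follow-up is 85–95% (C.4).

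**Assumptions.** Two-sided 5% level; ICC of 0.01, 0.02, 0.05 or 0.10, meaning correlation specific to a delivery group. The documents give neither.

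**The plan's own statement.** With independent observations, SE(d) near zero is √(1/40 + 1/20) = 0.274. The smallest d that reaches significance is t(0.975, 58 df) × 0.274 = 2.002 × 0.274 = 0.55. Power by the normal approximation is 45% at d = 0.5 and 83% at d = 0.8. This fits the plan's remark about medium to large effects, but only if clustering is ignored.

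**Standard error with clustering.**

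- Both arms: ratio of true to usual SE = √(1 + (m − 1) × ICC). At ICC 0.05 this is √1.45 = 1.20.
- PPPA groups only: ratio = √{[(1 + 9 × ICC)/40 + 1/20] / (1/40 + 1/20)}. At ICC 0.05 this is √(0.08625/0.075) = 1.07.
- 95% half-width for d = 0.548 × ratio.

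**Error rate of the usual tests.** These come from simulation with no treatment effect and four against two groups of 10. The t-test rows use a normal outcome. The branch rows assume two branches, each with two PPPA groups and one SPA group. The chi-squared rows assume 85% retention and beta-binomial counts.

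| ICC | 0 | 0.01 | 0.02 | 0.05 | 0.10 |
|---|---|---|---|---|---|
| SE ratio, both arms | 1.00 | 1.04 | 1.09 | 1.20 | 1.38 |
| Half-width for d, both arms | 0.55 | 0.57 | 0.60 | 0.66 | 0.76 |
| SE ratio, PPPA only | 1.00 | 1.01 | 1.03 | 1.07 | 1.14 |
| t-test error, both arms (%) | 5.0 | 6.1 | 7.2 | 10.4 | 15.8 |
| t-test error, PPPA only (%) | 5.0 | 5.4 | 5.8 | 6.8 | 8.8 |
| t-test error, half of the correlation shared by branch (%) | 5.0 | 5.5 | 6.1 | 7.6 | 10.3 |
| t-test error, all of it shared by branch (%) | 5.0 | 5.0 | 4.8 | 4.7 | 4.5 |
| Chi-squared error, both arms (%) | 4.5 | 5.4 | 6.3 | 9.4 | 14.3 |
| Chi-squared error, PPPA only (%) | 4.5 | 4.8 | 5.1 | 6.2 | 8.2 |

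ANOVA on two arms is the same test as the t-test.

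**Retention in percentage points.** At 85% in both arms the usual half-width is 1.96 × √(0.85 × 0.15 × 0.075) = 0.19, or 19 points. Multiplied by the both-arm ratio it becomes 20, 21, 23 and 26 points.

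**Two sensitivities.** The scale of the ICC matters for the binary outcome: at an assumed 80% retention and ICC 0.05, chi-squared error is 10.0% with a beta-binomial ICC but 7.3% if the ICC is on a latent scale. At 85% follow-up, m falls to 8.5 and the both-arm ratio at ICC 0.05 is √(1 + 7.5 × 0.05) = 1.17.

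**The case against.** **Not every within-group correlation does harm.** Aim 1 uses two YMCA branches, and Aim 2 follows Aim 1 procedures apart from listed exceptions, none of which concerns branches. Correlation from a branch or cohort that both arms share evenly cancels from the arm difference; in the simulated layout the t-test is then slightly conservative. This stands, and it limits the point to correlation specific to a delivery group. The documents do not give the actual layout.

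**The ICC may be small.** C.2.e describes one type of provider: a bachelor's-level "RI will conduct the treatment, with oversight from the investigative team". If one person leads every group, differences between therapists are absent. Manuals, fidelity checks and homework done individually by text point the same way. Group exchange of the kind in C.2.d ("In the final session, participants discuss their experiences with PPPA") is PPPA content, so clustering could be confined to that arm. All this is fair, but it does not remove shared sessions, peers and timing.

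**The plan is about effect sizes.** C.5 says so, warns against relying on small pilots and acknowledges large standard errors. It sets no alpha, margin or progression rule, so no planned decision is shown to change. This lowers the severity. It does not make the named tests correct, and C.5 does not connect its warning to group delivery.

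**Stronger readings the documents do not support.** A reader might infer that the estimated effects are biased; they are not, because clustering affects only their precision. A reader might infer that the planned intervals for Cohen's d are wrong; the plan states none. A reader might infer that the MVPA and mediator models ignore delivery group; their random effects are unstated, so such a term is neither included nor excluded and no error is shown there.

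**Conclusion.** The point holds in a limited form. The H1 ANOVA and chi-squared tests, followed as written, understate uncertainty if there is positive correlation specific to a delivery group. The same would apply to an ordinary interval later attached to unadjusted Cohen's d.

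The size rests on an assumed ICC. With equal clustering in both arms, t-test error is about 6–7% at ICC 0.01–0.02, which is small; it roughly doubles to 10% at 0.05 and reaches 16% at 0.10. With clustering in PPPA only, it is between about 5% and 9% over the same range. The chi-squared figures also rest on the assumed retention and on the ICC scale.

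Severity is minor to moderate: named tests with the wrong error bars, in a pilot that gives priority to effect sizes and attaches no decision to a threshold.

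**What to change.** Add to C.5:

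> *Treatment is delivered in six groups nested within arm. For sessions attended, CSQ-8 and retention, and for any interval reported for unadjusted Cohen's d, we will report the usual 95% interval and, as a sensitivity analysis, the interval with the standard error multiplied by √(1 + (m − 1) × ICC) at ICC 0.01, 0.05 and 0.10, where m is the mean number analysed per delivery group. ICC here means correlation specific to the delivery group, assumed equal in both arms.*

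Also state the random effects of the mixed models, and fit a delivery-group random intercept with small-sample degrees of freedom as a secondary analysis. Note that six groups estimate an ICC poorly, so an estimate of zero is not evidence of no clustering: in simulation the between-group variance estimate was zero or negative in 53, 49, 38 and 25% of trials at ICC 0.01, 0.02, 0.05 and 0.10.

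**Cost.** A few sentences and a small table. Group membership is known, each adjusted interval is a fixed multiple of the usual one, and design and sample size do not change. The adjusted intervals are wider and less favourable, depend on an assumed ICC, and are conservative if only PPPA groups cluster or if correlation is shared across arms. The random-intercept analysis has about 6 − 2 = 4 degrees of freedom, so its critical value is 2.78 instead of 2.00. Its intervals are then about 39% wider (2.78/2.00 = 1.39) even when the estimated ICC is zero, which is why it should remain secondary.
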